**Attachment Name Category Version Date Attached**

Needs Assessment for

[Navigator.rtf](#)

Subject Data Collection

Instruments 3 03/08/17

[Draft Follow-Up Survey.rtf](#) Subject Data Collection

Instruments 1 12/16/16

[3-month follow-up survey](#)

[IRB\\_coronavirus update.rtf](#)

Subject Data Collection

Instruments 4 03/09/20

[6 Month Follow-Up](#)

[Survey\\_coronavirus update.rtf](#)

Subject Data Collection

Instruments

8 03/09/20

[Final Baseline IRB\\_coronavirus update.rtf](#)

Subject Data Collection

Instruments 5 03/09/20

**1.16** Does this project involve creating any audio, video, or photographs?

Yes

**1.17** Does the study include any form of deception (e.g., providing participants with false information, misleading information, or withholding information about certain study procedures)?

Examples:

Procedure includes a cover story that provides a plausible but inaccurate account of the purposes of the research. Participants will be provided with false information regarding the particular behaviors of interest in the research.

Procedures include a confederate pretending to be another participant in the study.

Participants will be told that the research includes completion of a particular task, when in fact, that task will not be administered.

Study is designed to introduce a new procedure (or task) that participants are not initially told about.

No

**1.18** Indicate any payments or reimbursements to participants (check all that apply)

**Gift or Debit Card**

**1.19** Does this study have a plan to have an individual or committee review combined data from all participants on a periodic basis (such as summary or aggregate safety and/or efficacy data)?

No

**1.20** What have you done to minimize any risks?

- No foreseeable risks
- Psychological consultation and/or referrals readily available

**1.21** What are the potential benefits related to this project for:

the participant (if any)

benefits to society (if any)

All participants in the study will be given the opportunity to stop smoking with a quit coach from the Missouri Tobacco Quitline. Some participants, not all, may receive free Nicotine Replacement Therapy (NRT) as a result of their insurance status.

Participants in the control group will receive standard quitline services that include four quit coaching sessions, as well as a quit guide resource booklet.

Participants in treatment group 1 will receive standard quitline services that include four quit coaching sessions, as well as a quit guide resource booklet. Additionally, participants will be assigned to a Basic Needs Navigator that will assist them in navigating the resources provided to them on their previous 2-1-1 calls and addressing any other basic needs that have since require immediate attention.

Participants in treatment group 2 will receive a specialized quitline that includes four quit coaching sessions and an abbreviated quit guide tailored to the population.

Participants in treatment group 3 will receive a specialized quitline that includes four quit coaching sessions and an abbreviated quit guide tailored to the population. Additionally, participants will be assigned to a Basic Needs Navigator that will assist them in navigating the resources provided to them on their previous 2-1-1 calls and addressing any other basic needs that have since require immediate attention.

This study provides a significant health benefit to participants and their close others who were exposed to smoke. This research will allow us to examine the impact of two strategies for increasing smoking cessation among low income smokers.

The benefits of this study far outweigh the minimal risks of participation. Little published research to date has examined the relative effect of unmet basic needs navigation intervention on smokers' ability to complete quitline counseling, and successfully abstain from smoking for 7 or more days at 3 and 6 months follow-up. If the addition of the basic needs navigator's support significantly improves cessation rates of quitline clients, such supports could become integrated into standard quitline training and service.

Helping the Poor Quit Smoking: Specialized Quitlines and Meeting Basic Needs

NCT03194958

3/8/17

Provide a summary of the analysis methods you will use, including, if applicable, the data points or outcomes you will analyze.

Aim 1: For each group, descriptive statistics will show the proportion of baseline participants reached by the quitline, number of quitline sessions completed, and additional services (Print, Text2Quit, WebCoach) used. Differences by group will be compared using chi-square tests or logistic regression for categorical variables and by t-tests, linear regression or appropriate non-parametric tests for continuous variables. Secondary analyses will explore any differences by covariates such as gender, age, rural/urban residence, and unmet basic needs. Significant intervention and/or covariate effects will be included in all further analyses.

Aim 2: We will calculate quit rates for each group by dividing the number of participants who meet this criterion by the number of participants randomized to that group. Analysis will follow intent-to-treat (ITT) principles; all participants who completed a baseline assessment and were randomized will be included in analysis. Those lost-to-follow-up, refusing interviews, or otherwise unreachable will be assumed to be smokers. We will use logistic regression to compute odds ratios and 95% confidence intervals for group differences in quit rates, comparing Standard and Specialized Quitlines with and without a Basic Needs Navigator, with the “standard quitline, no navigator” group as the referent.

We will conduct analyses of secondary outcomes (7 and 30 day point prevalence abstinence, >24 hour quit attempt, use of pharmacotherapy, participation in cessation counseling) at 3 and 6 month follow up. Consistent with other reports in the literature, we also will compare the results from self-reported smoking cessation to results that adjust for biochemical validation. First, we will consider all participants who fail the biochemical validation and those that did not return a saliva sample to be smokers and recalculate abstinence rates by group. Second, we will recalculate abstinence rates by group, assuming that the true smoking cessation rate of participants who do not complete a follow up survey or do not return their saliva samples is the same rate as for those who did return a sample. Additionally, we will explore differences between people who do and do not agree to receive a kit and do and do not return a saliva sample. Analyses will be repeated with multiple logistic regression to include

potential baseline covariates (e.g., socio-demographics, rural/urban residence, nicotine dependence, readiness to quit). Cases with missing data on covariates will be excluded from analyses.

We also will conduct a series of sensitivity analyses to evaluate the robustness of our findings. To assess effects of protocol deviations, we will compare results of per-protocol analyses to ITT analysis. We will examine quit rate differences by intervention “dose” (i.e., number of completed quitline calls, number of navigator contacts), number of unmet basic needs, demographics, and smoking variables assessed at baseline, and extent of problem resolution at 3- and 6-month follow-up. We will assess the effect of missing data by comparing ITT results to a complete case (all data available at 6-month follow-up) analysis.

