**1.23**

Provide the rationale or power analysis to support the number of participants proposed to complete this study.

To be consistent with national reporting guidelines and evidence reviews, the primary cessation outcome will be 7-day point prevalence abstinence measured at 6-months post-baseline. With a baseline sample of 2000 smokers (500 per group) we will have sufficient power for detecting a 5% difference in quit rates between our most intensive condition (Specialized Quitline with Basic Needs Navigator) and least intensive (standard quitline without basic needs navigator) condition for a range of possible quit rates in the sample as a whole. Quit rates were based on the range of 6-month cessation rates from previous Alere clients. We conservatively expect to reach at least 60% of baseline participants at 6-month follow-up, leaving a total sample of at least 1,200 smokers. We would still have sufficient power to detect a 5% difference between groups if OR=1.8 with a total quit rate of 10%, and even greater power for lower quit rates and for intent to treat analyses that include all randomized participants, because non-respondents are assumed to have continued smoking thus overall quit rates would be lower.

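### The SAP leaves open whether the primary abstinence model is adjusted and for which covariates; a short covariate list fixed in advance would settle this and bring a small gain

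*SAP*

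**What the plan says.** Section 1.23 of the SAP fixes the outcome: "the primary cessation outcome will be 7-day point prevalence abstinence measured at 6-months post-baseline". Three statements elsewhere in the SAP bear on the model for it.

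- **Aim 2, main model.** "We will use logistic regression to compute odds ratios and 95% confidence intervals for group differences in quit rates", with the standard quitline without navigator as referent. No covariate is mentioned. The analysis set is intention-to-treat: "all participants who completed a baseline assessment and were randomized will be included in analysis". Missing outcomes are handled by rule: "Those lost-to-follow-up, refusing interviews, or otherwise unreachable will be assumed to be smokers".
- **Aim 1, last sentence.** After describing exploratory analyses of quitline use by covariates such as gender, age, residence and unmet basic needs, the SAP adds: "Significant intervention and/or covariate effects will be included in all further analyses".
- **Aim 2, adjusted repeat.** "Analyses will be repeated with multiple logistic regression to include" "potential baseline covariates (e.g., socio-demographics, rural/urban residence, nicotine dependence, readiness to quit". The next sentence reads: "Cases with missing data on covariates will be excluded from analyses".

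None of these is identified as the model that decides the primary comparison.

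**The concern.** The primary test should be determined by the plan and not by the data. Here the covariate content of the primary model depends on which sentence is followed.

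If the Aim 2 sentence stands alone, the primary test is unadjusted. Baseline measures the trial already plans to collect are then used only in a repeat with no fixed list, on a possibly smaller sample. If the Aim 1 sentence governs, covariates enter the primary model because they were significant for quitline use. That is a different outcome, and the selection is driven by the data. The exclusion rule would then also remove participants from a model that the SAP says includes everyone randomized with a baseline assessment.

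At stake are pre-specification and a modest amount of power in a comparison that has none to spare.

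**Working it through.** **1. Reading the sentences together.** The Aim 1 rule refers to all further analyses, and Aim 2 comes next, so on its literal terms it reaches the primary model. The Aim 2 model sentence is silent on covariates, and the word *repeated* in the adjusted analysis implies that the first run had none. Both readings are tenable. The examples in the Aim 1 list do not include nicotine dependence or readiness to quit; those appear only in the repeat. Both lists are illustrative.

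**2. The plan's own effect size.** SAP 1.23 gives OR 1.8, a 10% total quit rate and a 5-point difference. Solving for two rates with mean 10% and OR 1.8 gives 7.4% and 12.6%, a difference of 5.2 points. Conversely, 7.5% vs 12.5% gives OR (0.125/0.875)/(0.075/0.925) = 1.76. These inputs agree. No numerical power or alpha is stated, so there is no power figure to reproduce. I assume two-sided 0.05, in line with the 95% intervals.

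**3. Starting power, most vs least intensive group.** Power = Φ[(Δ − 1.96·SE₀)/SE₁], where SE₀ = √(2·0.10·0.90/500) = 0.01897 and SE₁ = √((0.075·0.925 + 0.125·0.875)/500) = 0.01891. This gives Φ[(0.05 − 0.0372)/0.01891] = Φ(0.68) = 0.75. With 7.4% vs 12.6% it is 0.78. At 300 per group (60% of 2000 = 1200, over four groups) the two figures are 0.53 and 0.56. Power of 80% needs 564 or 526 per group.

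**4. What adjustment changes.** Simulation with 500 per group, marginal rates held at 7.5% vs 12.5%, one standard-normal baseline covariate, Wald tests and 2,500 trials per setting (Monte Carlo error about 1 point). AUC and the share of cases excluded are assumptions; the documents give neither. As a check on the unadjusted columns, log OR = ln 1.76 = 0.57 and SE = √(1/37.5 + 1/462.5 + 1/62.5 + 1/437.5) = 0.217.

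| AUC | Unadjusted log OR / SE | Adjusted log OR / SE | Power, unadjusted | Power, adjusted, all kept | Power, adjusted, 5 / 10 / 15% excluded |
|---|---|---|---|---|---|
| 0.58 | 0.567 / 0.219 = 2.59 | 0.572 / 0.220 = 2.60 | 0.740 | 0.744 | 0.730 / 0.702 / 0.672 |
| 0.64 | 0.574 / 0.219 = 2.62 | 0.587 / 0.222 = 2.64 | 0.755 | 0.762 | 0.730 / 0.709 / 0.691 |
| 0.71 | 0.572 / 0.219 = 2.61 | 0.610 / 0.226 = 2.70 | 0.754 | 0.779 | 0.761 / 0.734 / 0.720 |
| 0.77 | 0.572 / 0.219 = 2.61 | 0.643 / 0.233 = 2.76 | 0.757 | 0.804 | 0.777 / 0.768 / 0.729 |

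The standard error of the log OR rises. Power improves because the conditional estimate moves further from zero than the standard error grows. A separate set of 4,000 trials per setting gave 0.745 to 0.750, 0.747 to 0.776 and 0.755 to 0.797 at AUC 0.64, 0.71 and 0.77. In that set the variance of the standardized risk difference was about 1%, 6% and 10% below the unadjusted one.

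**5. Rates with non-respondents counted as smokers.** If 60% respond in each group, 0.6 × 7.5% = 4.5% and 0.6 × 12.5% = 7.5%. At 500 per group, power goes from about 0.51 to between 0.51 and 0.53. A further run put the gain at 0 to 3 points.

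**6. Effect of excluding cases.** Losing 5% of cases wipes out the gain at AUC 0.64 and most of it at 0.71. Losing 10% wipes it out at both.

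**The case against.** An unadjusted intention-to-treat comparison is valid in a randomized trial, and the adjusted repeat already addresses chance imbalance. Which of the two is called primary could be seen as taste. At the rates produced by counting non-respondents as smokers, the gain is barely above simulation error. Everyone analysed completed a baseline assessment, so few cases may lack covariates. All of this stands, and it is why the point is minor. It does not answer the question of which model is primary, or the use of significance on other outcomes to choose covariates.

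A reader might infer more than the documents support:

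- *That the primary model is definitely unadjusted.* The Aim 1 carry-forward sentence prevents that conclusion.
- *That strong predictors are being ignored.* The SAP calls them potential covariates and gives no prognostic strength. Entry is limited to daily smokers planning to quit within 30 days (protocol 1.7), which narrows the spread of readiness.
- *That precision of the odds ratio is lost.* On the log-OR scale adjustment widens the standard error. The gain is in power and in the precision of the risk difference.
- *That the result would be biased.* Nothing here shows bias in the unadjusted comparison.
- *That the repeat loses many participants.* The exclusion rule is explicit, but its size is unknown.

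**Conclusion.** The point holds as one of pre-specification with a small efficiency gain attached. The SAP does not determine whether the primary abstinence model is adjusted, and neither reading yields a covariate list fixed in advance.

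Over assumed AUCs of about 0.6 to 0.77 with 500 per group, adjustment on the full sample is worth about 0 to 5 points of power at 7.5% vs 12.5% and about 0 to 3 points at 4.5% vs 7.5%. The variance of the risk difference falls by roughly 1 to 10%. These figures rest on two-sided 0.05, one normal covariate, and prognostic strength that the documents do not give.

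Adjustment should not be presented as the remedy for low power. Against a conventional 80% (the SAP states no target), the pairwise comparison reaches about that level only at 500 per group, with 7.5% vs 12.5% and the strongest covariate assumed. At 300 per group, or at 4.5% vs 7.5%, it stays far short. That shortfall is a separate sample-size matter.

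**What to change.** Amend the SAP, before anyone sees outcomes by group, to state:

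- The primary model is logistic regression on study group plus a short fixed list: baseline nicotine dependence, readiness to quit and number of unmet basic needs, with the coding of each given.
- The Aim 1 rule on significant covariates does not apply to Aim 2.
- All randomized participants stay in the model. Missing baseline covariates are handled by simple baseline imputation or a missing indicator, in place of case exclusion.
- Standardized quit rates and risk differences are reported beside the odds ratio, with a note that the adjusted odds ratio is conditional on the covariates.
- The unadjusted comparison is reported as supportive.

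This needs SAP wording and a little programming, and no new data. Keeping all participants is an essential part of it, because excluding even 5 to 10% of cases could cancel the gain.

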For participants completing the urine test, verbal consent will be obtained over the phone, prior to mailing the testing kit. Participants will be contacted within 1-2 business days of completing the 6-month follow-up survey to consent to the urine test and review instructions. The urine test will be offered to all participants who reported smoking abstinence at 6-month follow-up.

Re-consenting of participants regarding the audio recordings will take place by telephone and documented in their study record. This language has been modified in the updated consent document that has been uploaded.

**1.13** Provide a detailed description in sequential order of the study procedures following the consent process - DO NOT cut and paste from the Consent Document.

Describe study populations separately if they will be participating in different procedures

DESCRIBE:

Control populations, if applicable

Any randomization, if applicable

What participants will be asked to do/what happens in the study (in sequential order)

The time period over which procedures will occur

Long-term follow-up and how it occurs

The recruitment and study procedures will occur for about 3 years. Participants will be asked to participate in the study for a total of six months that will include completing the quitline coaching sessions which can take 1-4 months, and follow-up at 3 and 6 months; however, they can withdraw from the study at any time. During this time, half of the participants will also be asked to work with a Navigator to assist with the basic needs from their initial 2-1-1 call.

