All participants who complete the 6-month follow up survey (estimated N=1200) and report smoking abstinence and no use of nicotine replacement products in the past 7 days (estimated <14% = N<168) will be invited to biochemically assess carbon monoxide levels or cotinine levels. If participants are willing to participate, they will be mailed a urine test to measure their cotinine levels, which is a metabolite of nicotine. The urine test, which can be purchased at any local pharmacy over-the-counter, will be mailed to participants with instructions for sending the results. The study team will not receive any biological samples or testing materials in the mail. Instead, participants will be instructed to send a picture of their results to the study email account and/or phone account. The photo will include only the results: a photo of the dipstick next to the results card. No personal identifiable information will be included in the photo. The results will be linked to the participants study ID via their phone number from which the photo was sent. Consent will be obtained prior to sending the testing kit in the mail via phone script (see attached). Results will be recorded in participants study record. Incentives will be mailed to participants after result has been received by study team.

**1.14** Will participants be randomized?

Yes

**1.15** Will any of the following be used to collect information from the participant or others?

Screening questions or screening/eligibility questionnaires

Surveys

Questionnaires

Stimuli

Any other written assessments

Yes

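### The SAP scores biochemical validation on returned saliva samples, but the protocol collects photographed urine tests and leaves unclear who is offered one, so abstainers never offered a kit would count as smokers

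*SAP*

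**What the plan says.** The SAP's Aim 2 analysis compares self-reported quitting with rates adjusted for biochemical validation. Three elements depend on saliva:

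- First recalculation: "First, we will consider all participants who fail the biochemical validation and those that did not return a saliva sample to be smokers".
- Second recalculation: the true cessation rate of people who miss the follow-up survey or "do not return their saliva samples is the same rate as for those who did return a sample".
- Exploratory comparison: people who "do and do not agree to receive a kit and do and do not return a saliva sample".

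Protocol 1.13 describes a different procedure. If participants are willing, "they will be mailed a urine test to measure their cotinine levels, which is a metabolite of nicotine". Then "participants will be instructed to send a picture of their results to the study email account and/or phone account", the picture showing the dipstick beside its results card. It adds: "The study team will not receive any biological samples or testing materials in the mail". The result is entered in the study record.

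The protocol gives two accounts of who is tested. Section 1.12 says: "The urine test will be offered to all participants who reported smoking abstinence at 6-month follow-up". Section 1.13 restricts the invitation to six-month completers who report abstinence and have used no nicotine replacement over the preceding 7 days, with an estimate of under 14%, or fewer than 168 of 1,200. Section 1.13 also says these people "will be invited to biochemically assess carbon monoxide levels or cotinine levels", although the urine test is the only procedure it describes.

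**The concern.** The SAP's scoring rule names a specimen that is not collected and an act, returning it, that does not take place. The SAP mentions neither urine nor a dipstick nor a photo. It therefore does not say what counts as a returned result, a failed result or an unusable one.

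A second gap remains after the specimen name is corrected. The first recalculation has only two routes to smoker status, failing or not returning, and no category for an abstainer who was never sent a kit. Under Protocol 1.13 that group exists by design.

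At stake is the only check on self-reported quitting that the documents describe. If scoring is settled after results are seen, the validated rates are open to choice. If abstainers using nicotine replacement are counted as smokers by default, those rates are too low. The distortion could also differ by arm if nicotine replacement use does. Protocol 1.4 asks whether use of cessation medication varies by study group, so this cannot be assumed away; nothing in the documents shows that it happens.

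**Working it through.** **1. The plan's own figures.** Inputs: 2,000 randomized, 500 per group, at least 60% reached at six months (SAP 1.23); under 14% of completers invited to test (Protocol 1.13).

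- Completers: 2,000 × 0.60 = 1,200, as stated.
- Invited, upper bound: 1,200 × 0.14 = 168, as stated. That is 42 per arm if spread equally (168 / 4), and 168 / 2,000 = 8.4% of those randomized, the denominator that the SAP uses for quit rates.

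The 168 bounds the people invited under 1.13. It is not a count of all self-reported abstainers, because abstainers using nicotine replacement are left out of it.

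**2. The texts side by side.**

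| Item | SAP, Aim 2 | Protocol |
|---|---|---|
| Specimen | Saliva | Urine cotinine (1.12, 1.13); carbon monoxide named, no procedure given (1.13) |
| What comes back | A sample | A photo; no specimens received (1.13) |
| Failure | Not defined | Dipstick shown beside results card (1.13) |
| Who is tested | Not stated | All abstainers (1.12); abstainers without recent nicotine replacement (1.13) |

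**3. Literal reading.** Saliva samples returned = 0. The first recalculation scores every self-reported abstainer as a smoker, giving 0 / 500 in each arm and no estimable odds ratio. The second needs a rate among returners, which is 0 / 0. The returner group in the exploratory comparison is empty.

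**4. Sensible reading: saliva sample means kit result.** Validated quitters = 168 × r × c, where r is the share sending a usable photo and c the share of those confirmed. The documents give neither, so both are assumed: r from 30% to 100%, c from 60% to 100%.

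- Low: 168 × 0.30 × 0.60 = 30.2, or 1.5% of 2,000.
- High: 168 × 1.00 × 1.00 = 168, or 8.4% of 2,000.

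The validated rate can be calculated on this reading. It depends on what counts as a usable photo and as a positive result, which the SAP does not settle.

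**5. Abstainers not offered a kit.** Let s be the share of all self-reported abstainers who used nicotine replacement in the preceding 7 days. If the other abstainers number 168, the uninvited number 168 × s / (1 − s).

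| s (assumed) | All abstainers | Not offered a kit | Self-reported rate (of 2,000) | Highest validated rate, first rule |
|---|---|---|---|---|
| 0% | 168 | 0 | 8.4% | 8.4% |
| 10% | 186.7 | 18.7 | 9.3% | 8.4% |
| 20% | 210 | 42 | 10.5% | 8.4% |
| 30% | 240 | 72 | 12.0% | 8.4% |

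The last column assumes that every invited person returns a confirming result. So at s = 30% the validated rate falls 3.6 percentage points below self-report with no test failed or missing. Because 168 is an upper bound, the counts shrink in proportion if fewer are invited.

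Following 1.12 instead does not remove the problem. The protocol itself describes cotinine as coming from nicotine, so an abstainer on nicotine replacement could test positive and be scored as failing.

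**The case against.** The strongest reply is that nobody would apply the saliva wording literally. The SAP speaks of agreeing to receive a kit, which matches the testing kit mailed under the protocol, and Protocol 1.13 says that results are recorded. An analyst would very probably substitute the kit result. This stands. A reader might infer that the trial is set to report 0% validated abstinence in all four arms, or that the validated rates cannot be obtained from the data collected. The documents support neither; step 3 shows what the words say, not an expected result.

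It can also be said that the SAP is dated 3/8/17 while Protocol 1.15 lists survey attachments dated 03/09/20, so the saliva wording may predate the urine procedure. That is plausible but an inference. It would explain the mismatch without removing it.

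Third, failure is arguably not tied to saliva at all: the SAP speaks of failing validation, and the results card supplies a reading standard. This largely stands. Nothing suggests that several kits with different cut-offs would be used. What is missing is a sentence linking the SAP to that card.

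Finally, the uninvited group may be small. The standard quitline in Protocol 1.13 supplies at most two weeks of nicotine replacement, so use just before the six-month survey may be uncommon, and s may lie below 10%. That limits the likely size but leaves the group without a scoring rule.

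**Conclusion.** The concern holds in a limited form. The SAP and protocol conflict on specimen, on what is returned and, within the protocol, on who is tested. The specimen conflict would probably be resolved by a sensible analyst. The scoring of abstainers who are never offered a kit would not, because the rule as written sends them to smoker status.

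The size rests on an assumed share of nicotine replacement users: none at 0%, about 19 people at 10% and 72 at 30%, each alongside 168 others and taking Protocol 1.13 as the operative rule.

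Only the biochemically adjusted comparison is affected. A reader might infer that the main result is compromised. It is not: the primary outcome is self-reported 7-day abstinence at six months (Protocol 1.3), and its analysis makes no use of the test. This is a secondary-analysis defect that should be corrected, and cheaply can be.

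**What to change.** In the SAP's Aim 2 analysis:

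- Replace return of a saliva sample, wherever it occurs, with sending a readable photo of the urine cotinine test result.
- Define failure as a positive reading on the kit's results card, and treat an unreadable photo as not returned.
- State that abstainers not offered the test count neither as failures nor as non-returners. One option is to keep their self-report in the adjusted rates and add a sensitivity analysis that scores them as smokers. Report their number by arm.

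In the protocol:

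- Reconcile 1.12 and 1.13 on who is offered the test. If abstainers using nicotine replacement are to be tested, the SAP must also say how a positive result among them is scored.
- Reconcile the mention of carbon monoxide in 1.13 with the urine procedure, the only one described. Which way is for the sponsor to decide.

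The cost is SAP and protocol wording and a little more analysis; no new participant procedure is needed. Keeping self-report for uninvited abstainers leaves some unverified quitters in the adjusted rate, which is why the sensitivity analysis should accompany it.

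### The second biochemical recalculation spreads a rate from under 42 kit returners per arm over 200 or more people, with no rule for pooling, uncertainty or person-level outcomes

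*SAP*

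**What the plan says.** SAP Aim 2 plans two recalculations that adjust self-reported abstinence for biochemical validation. The first counts failed and unreturned tests as smoking. The second reads "Second, we will recalculate abstinence rates by group, assuming that the true smoking cessation rate of participants" who lack a follow-up survey or a returned sample matches the rate among those who returned one. It does not say whether the returners' rate is taken over all arms or within each arm, and it gives no imputation step or variance method.

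Two other sentences in Aim 2 matter. For the intention-to-treat quit rates: "We will use logistic regression to compute odds ratios and 95% confidence intervals for group differences in quit rates". After the biochemical text: "Analyses will be repeated with multiple logistic regression to include" baseline covariates. Whether the second sentence covers the second recalculation is not stated.

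On numbers, SAP 1.23 has "With a baseline sample of 2000 smokers (500 per group"), then "We conservatively expect to reach at least 60% of baseline participants at 6-month follow-up", "leaving a total sample of at least 1,200 smokers". Protocol 1.13 limits testing to six-month completers who report abstinence and "no use of nicotine replacement products in the past 7 days (estimated <14% = N<168").

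**The concern.** The returners' rate is itself an estimate from a small sample, yet it would supply the outcome for a large part of each arm. Entering the filled-in people as if their outcomes had been observed ignores the sampling error of that rate.

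The rule also yields a group total such as 161.3 abstainers out of 500, not a yes/no outcome per person, so a logistic model cannot be fitted to it without further invention. The first recalculation has no such difficulty, because it gives everyone a status.

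Finally, everyone invited to test has already reported abstinence. Their confirmation rate answers a different question from the abstinence rate of people who never completed a survey.

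At stake is one of the two checks on whether the self-reported result survives validation. Chance differences between a few kits per arm could look like an arm effect, or like a contradiction of the self-reported result. Under a different choice of rate, a real difference could be hidden.

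**Working it through.** **The plan's own figures.** 0.60 × 2000 = 1200 completers, and 0.14 × 1200 = 168 invited; both match the documents. Per arm: 500 randomised, R = 300 surveyed, 200 not surveyed, and fewer than 168/4 = 42 invited. At most 168/2000 = 8.4% of participants can supply a test result.

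**Notation, per arm.** Q = self-reported abstainers, T = kits returned, V = confirmed, c = V/T. Respondents who report smoking stay smokers.

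- Literal rule: count = V + (Q − T)c + (500 − R)c = c(Q + 500 − R).
- Alternative: with x = V + (Q − T)c, non-completers get the validated rate among respondents, so count = x + (500 − R)x/R.

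**Worked example** (assumed: Q = 42, T = 21, V = 14, arm-specific rate).

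- Literal: 14 + (2/3)(21 + 200) = 161.3, or 32.3% of 500.
  - Naive 95% half-width: 1.96 × √(0.323 × 0.677/500) = 4.1 points.
  - Propagated: A = 242/500 = 0.484; var(c) = (2/3)(1/3)/21 = 0.01058; var(A) = 0.484 × 0.516/500 = 0.00050. The half-width is 1.96 × √(A²·var(c) + c²·var(A)) = 10.2 points, 2.5 times the naive one.
- Alternative: 28/300 = 9.3%.
  - Naive: 1.96 × √(0.0933 × 0.9067/500) = 2.5 points.
  - Propagated: 1.96 × √(0.14² × 0.01058 + (2/3)² × 0.14 × 0.86/300) = 3.8 points, 1.5 times the naive one.

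**Simulation with no true arm difference.** R ~ Bin(500, 0.6), Q ~ Bin(R, 0.12), T ~ Bin(Q, return), V ~ Bin(T, confirmation), with four arms and 40,000 runs. Two arms are compared by a Wald test on the log odds ratio, counting 500 observed per arm. The 12% self-reported abstinence, 40-80% return and 70-85% confirmation are assumptions; the documents give none of them.

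| Fill | Rejection at nominal 5% | True SD of log OR | Naive SE |
|---|---|---|---|
| Literal, arm-specific rate | 24-49% | 0.22-0.41 | 0.13-0.14 |
| Alternative, arm-specific | 13-22% | 0.28-0.39 | 0.21-0.23 |
| Only the confirmation rate pooled; non-completers get own arm's validated rate | 9-12% | 0.26-0.29 | 0.21-0.23 |
| Literal, rate pooled over arms | 1-3% | 0.10-0.11 | 0.13-0.14 |

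If the alternative is pooled throughout, rejection is about 0.4-1%. With wider assumptions (14% eligible, 30-80% return, 50-90% confirmation), the arm-specific ranges become 18-60% (literal) and 13-32% (alternative). The fully pooled fills reject 0.1-3.3%.

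**Level.** With 12% of 300 = 36 abstainers per arm, the literal rate is c(36 + 200)/500 = 0.472c. That is 33% at c = 0.70 and 40% at c = 0.85. Self-reported abstinence is 12% among respondents and 0.12 × 0.6 = 7.2% with non-respondents counted as smokers. The alternative gives 0.12c, or 8.4-10.2%.

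**The case against.** The strongest reply is that the SAP announces recalculated rates and nothing more. It does not say that filled-in counts will be tested, given confidence intervals or treated as observed. The sentence on logistic regression in the intention-to-treat text concerns a different analysis. The later one on repeated analyses follows several items that do have person-level data. This stands: the documents leave the variance method unstated; they do not specify a wrong one. The SAP also cites sources for the rule, which may describe a method but cannot be judged here.

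A reader might infer that the intervals will be far too narrow whichever rate is used. The documents do not support that. The text fits a rate pooled over arms as well as an arm-specific one. Under full pooling the shared error largely cancels between arms and the fill pulls them together, so between-arm intervals are too wide. The wording by group makes the arm-specific reading natural but does not settle it.

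A reader might also infer that the trial's main conclusion is exposed. It is not. The primary outcome is self-reported 7-day abstinence at six months with missing counted as smoking, and the first recalculation needs no estimated rate.

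It may also be said that the inflated level matters more than precision. That is fair. But correcting the level alone leaves 13-22% rejection with arm-specific rates, so both need attention.

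**Conclusion.** The concern holds as an under-specified and, read literally, unsuitable rule for a supporting analysis. Three things follow from the documents alone: the rate rests on fewer than 42 people per arm even with full return, no method carries its uncertainty forward, and the result is a fractional group count.

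The size of the error is conditional on the filled-in counts being compared as 500 observed outcomes per arm, and on the assumed inputs. Its direction depends on whether the rate is pooled, with rejection from about 24-49% (literal, arm-specific) down to about 1-3% (literal, pooled) for a nominal 5% test. None of the fills examined gave correct between-arm inference. The inflated level, about 33-40%, needs no inferential step: it follows from applying abstainers' confirmation rate to survey non-completers. The change should be made, with medium confidence in the magnitudes.

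**What to change.** Amend SAP Aim 2 to separate the two kinds of missing outcome.

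1. Apply the confirmation rate from returners only to self-reported abstainers without a test result. State how this treats abstainers using nicotine replacement, whom Protocol 1.13 does not invite to test.
2. Impute survey non-completers from survey respondents in the same arm.
3. Carry this out by person-level multiple imputation within arm, drawing the model parameters afresh in each of about 50 imputations. Fit the planned logistic model to each data set and combine by Rubin's rules. Alternatively, bootstrap the whole recalculation within arm, re-estimating every rate in each resample. With so few returners, the confirmation model can support few covariates.
4. Report any validated odds ratios and 95% confidence intervals only from this procedure. If the recalculated rates are meant to be descriptive, say so; steps 1 and 2 are still needed to correct the level.

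The cost is SAP wording and modest programming, with no new data. Intervals will be wider than a naive arm-specific analysis would show.
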